1 BACKGROUND AND RATIONALE

Hypertensive disorders of pregnancy are a major cause of maternal morbidity and mortality, and it is felt that at least a portion of these adverse outcomes are preventable¹. Worldwide, between 2 and 8 percent of pregnancies are complicated by preeclampsia². Additionally, 0.9 to 1.5 percent of pregnant women have pre-existing chronic hypertension³. Postpartum hypertension can either be due to an exacerbation of existing chronic hypertension or preeclampsia, or it can be new onset^{2,4}. Blood pressures tend to increase in the postpartum period, peaking at three to six days postpartum. It is not uncommon for women who did not require medications during the pregnancy to be started on an antihypertensive in the postpartum period^{3,5}. If blood pressures are greater than or equal to 150 mmHg systolic and/or 100 mmHg diastolic on two occasions four to six hours apart, antihypertensive therapy is recommended^{4,6,7}.

The most commonly used antihypertensive medications in the postpartum period are labetalol and nifedipine ER. Studies have shown that nifedipine ER is at least as effective, and potentially even more effective, than labetalol in achieving blood pressure control^{4,7}. However, significantly more patients have side effects when taking nifedipine ER (48% versus 20%), and 24% of women using nifedipine ER report headache as a side effect⁷. Headache is a known symptom of preeclampsia, and its presence as a symptom can change patient management. When patients are using nifedipine ER, it can be difficult to determine if the headache is due to the medication or the disease, making management decisions difficult.

Like nifedipine ER, amlodipine is a dihydropyridine calcium channel blocker⁸. Headache is not a commonly reported side effect of amlodipine. Amlodipine is not commonly used in the postpartum setting, but a prior study in the non-obstetrical population demonstrated that amlodipine and nifedipine ER resulted in comparable reductions in blood pressure and can be considered equivalent. Amlodipine was also found to have a significantly lower rate of side effects than nifedipine ER (27% versus 41%)⁹.

Nifedipine ER is considered safe in breastfeeding women. Typically, a relative infant dose (RID) less than 10% is considered safe, and nifedipine ER has a RID of 2.3%. There is limited data on amlodipine use in breastfeeding women, and therefore the LactMed Database currently recommends an alternative to amlodipine if possible. However, one study has shown that the median RID for amlodipine is 4.18%, suggesting it is safe to use in breastfeeding women. In addition, multiple case reports of breastfeeding mothers using amlodipine did not demonstrate any adverse effects in the infant¹⁰. Although further data should continue to be collected, these prior studies and case reports are reassuring.

We hypothesize that amlodipine will be as effective as nifedipine ER in controlling blood pressures in patients with postpartum hypertension, as reflected by equivalent times from delivery to hospital discharge. In addition, we hypothesize that women taking amlodipine will report fewer side effects than those taking nifedipine ER. No effects on breastfeeding outcomes are expected.

1.1 Description of Intervention

Amlodipine and nifedipine ER are both dihydropyridine calcium channel blockers. In women with hypertensive disorders who meet criteria for initiation of treatment as outlined above, the allocated treatment will be initiated by the inpatient clinical team. The recommended starting dose for nifedipine ER will be 30 mg daily and the recommended starting dose for amlodipine will be 2.5 mg daily. Doses will be adjusted as needed by the clinical team. Patients will be treated with additional short-acting antihypertensives, additional long-acting antihypertensives or intravenous magnesium for seizure prophylaxis as would otherwise be clinically indicated.

2 STUDY OBJECTIVE

2.1 Primary Objective

The primary hypothesis of this study is that amlodipine is noninferior to nifedipine ER in the management of postpartum hypertension, as evidenced by length of stay from delivery until hospital discharge. A noninferiority limit of 24 hours was selected as a clinically relevant difference.

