Safety Evaluations	While hospitalized, patients will be monitored daily by the clinical team to assess for side effects and ensure adequate blood pressure control. Adjustments will be made by the clinical team as indicated based on patient status. After hospital discharge, patients will be able to call the office with any concerns and additional appointments for evaluation can be made as necessary.
Statistical and Analytic Plan	Noninferiority of amlodipine will be assessed with Wilcoxon Rank-Sum

Data and Safety Monitoring Plan	Participants will be provided with contact information for the PI should they have any concerns.
--	--

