4.1 Screening procedure

Women will initially be screened for study participation at the time of admission to Greenville Memorial Hospital's Family Birthplace unit. Additionally, women who do not initially meet criteria will be rescreened daily for the development of a new hypertension diagnosis. Women will be consented for enrollment and randomized at the time of admission or at time of diagnosis to ensure maximum trial participation. Not all women who are initially consented will meet criteria for final inclusion in the study and initiation of the study drug. Based on review of historical data, approximately 50% of patients who meet diagnostic criteria will eventually meet criteria for medication administration.

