5 STUDY EVALUATIONS AND MEASUREMENTS

-Demographic characteristics and clinical data will be abstracted from the medical chart

-Maternal age

-Gestational age at delivery

-Race

-BMI

-Parity

-Mode of delivery

-Hypertensive diagnosis

-History of diabetes (gestational or pre-gestational)

-Length of stay from delivery until discharge

-Number of acute antihypertensive treatments

-Number of dose increases of initial study drug

-Number of additional long-acting antihypertensives started

-Magnesium use

-Side effects reported

-Medication discontinuation

-Discharging physician

-Blood pressure at blood pressure check appointment

-Blood pressure at postpartum visit

- Readmissions from time of discharge until postpartum visit
- Breastfeeding status at time of postpartum visit
- Patient-reported length of breastfeeding
- Patient-reported breastfeeding satisfaction

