6 STATISTICAL CONSIDERATION

6.1 Sample size calculation

An initial power calculation was performed using a standard deviation of 55.2 hours and a non-inferiority limit of 24 hours; to achieve 80% power with a 2-tailed alpha of 0.05, 66 women would be needed in each arm.

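### The only stated primary analysis is an unadjusted rank-sum test that uses neither the randomization stratum nor mode of delivery; this gives up some precision, probably a modest amount, and introduces no bias.

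*Combined protocol and SAP*

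**What the plan says.** Section 2.1 defines the primary outcome as "length of stay from delivery until hospital discharge" and adds: "A noninferiority limit of 24 hours was selected as a clinically relevant difference". The only sentence on the primary analysis is in the synopsis, in the row for the statistical and analytic plan: "Noninferiority of amlodipine will be assessed with Wilcoxon Rank-Sum". Section 6 contains the sample size calculation and nothing else.

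Section 3.2 stratifies the 1:1 randomization by chronic hypertension status. Section 5 lists "Mode of delivery" among the items abstracted from the chart. Neither factor is given a role in the analysis.

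Under Section 4.2, study drug starts once a woman meets the pressure criteria, and the synopsis excludes women who took antihypertensives before delivery. Every treated woman therefore has some untreated hours inside her outcome. The time of first dose is not on the Section 5 list.

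**The concern.** Stay after delivery can vary for reasons unrelated to the drug. If mode of delivery or chronic hypertension status predicts stay, an unadjusted test leaves that predictable variation in its error term. If the stratum predicts stay, stratifying the randomization and then ignoring the stratum also tends to make the test conservative.

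In a noninferiority trial, lost precision means a wider interval, and so a higher chance that a truly equal drug fails to clear the 24-hour limit. This matters most at one-sided 0.025, which is what the stated two-tailed 0.05 implies and where the trial has no power to spare.

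**Working it through.** **Inputs from the documents.** SD 55.2 h, limit 24 h, 80% power, two-tailed alpha 0.05 and 66 per arm (Section 6.1); 160 women, so 80 per arm (Section 3.3). True difference taken as 0.

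**Inputs assumed.** The documents give no R², no cesarean share and no difference in stay by mode of delivery. I take 30-50% cesarean and a difference of 24 or 48 h.

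**Step 1: reproduce the plan's figure.** n per arm = 2 × (55.2/24)² × (z_α + z_0.80)² = 10.58 × (z_α + 0.842)².
- One-sided 0.05: 10.58 × (1.645 + 0.842)² = 65.4, so 66. This matches.
- One-sided 0.025: 10.58 × (1.960 + 0.842)² = 83.04, so 84. This does not match.

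The stated 66 corresponds to one-sided 0.05, although Section 6.1 says "to achieve 80% power with a 2-tailed alpha of 0.05". That mismatch is a separate point; here I show both levels.

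**Step 2: R² from mode of delivery.** R² = p(1 − p)d² / 55.2², where p is the cesarean share, d the difference in hours, and 55.2² = 3047.
- d = 24: 121/3047 = 0.040 at p = 0.3; 144/3047 = 0.047 at p = 0.5.
- d = 48: 484/3047 = 0.159 at p = 0.3; 576/3047 = 0.189 at p = 0.5.

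I carry forward the upper ends, rounded to 0.05 and 0.19.

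**Step 3: power.** SE = 55.2 × √(1 − R²) × √(2/n); power = Φ(24/SE − z_α).

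| n per arm | R² | SE (h) | 24/SE | Power, one-sided 0.05 | Power, one-sided 0.025 |
|---|---|---|---|---|---|
| 66 | 0 | 9.61 | 2.498 | 80% | 70% |
| 66 | 0.05 | 9.37 | 2.563 | 82% | 73% |
| 66 | 0.19 | 8.65 | 2.775 | 87% | 79% |
| 80 | 0 | 8.73 | 2.750 | 86.5% | 78.5% |
| 80 | 0.05 | 8.51 | 2.821 | 88% | 81% |
| 80 | 0.19 | 7.86 | 3.055 | 92% | 86% |

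Any further gain from the chronic hypertension stratum is not counted, because nothing in the documents sizes it.

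**Step 4: does the gain survive with a rank test on skewed stays?** Step 3 is normal theory for means, whereas the plan uses ranks. In a simulation with lognormal stays (assumed means 84-120 h, 40% cesarean, 66 per arm, one-sided 0.025), stratifying the margin-shifted rank-sum test by mode of delivery raised power in every scenario. At a mean of 100 h, power rose from about 86% to 89% for a 24 h difference and from about 82% to 94% for 48 h. A rerun with independently written code agreed to within about 2 percentage points.

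**Step 5: would a regression on hours do better than the rank test?** Not necessarily. With lognormal stays and the same assumed means, the unadjusted margin-shifted rank-sum test had 83-93% power, against 71-72% for an unadjusted comparison of means. Adjustment at R² 0.05-0.19 brings the mean comparison to only about 73-79% (Step 3).

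**The case against.** The strongest reply is that this is a preference about efficiency and not a defect. An unadjusted randomized comparison is valid, nothing in the plan is contradicted, and no R² in the documents shows that the gain is worth having. At the lower assumption the gain is 2-3 percentage points. With 80 per arm at one-sided 0.05, power is already about 86.5%. All of this stands, and it is why the point is a modest one. What remains is that both factors will already be in the data set, so the improvement costs almost nothing.

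A second reply is that mode of delivery can follow randomization, because Section 4.1 allows randomization at admission. That is true, but it is settled before any study drug is given, and the assigned postpartum drug is unlikely to affect it.

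A reader might also infer more than the documents support:
- **That the untreated hours bias the result, or that the clock must start at first dose.** Hours before the drug do not by themselves shift the difference between randomized arms. Time to the qualifying pressure or first dose arises after unmasked randomization and could be influenced by knowledge of the assignment, so it should not enter the primary analysis.
- **That removing untreated hours would give much larger gains.** If those hours had SD 12, 24 or 36 h (assumed), they would make up 5%, 19% or 43% of the variance (s²/3047), and power at 66 per arm would reach 82%, 87% or 95% at one-sided 0.05. This requires that they be independent of the remaining stay. If each later hour shortened the remaining stay by half an hour, the shares would be a quarter as large: 1%, 5% and 11%. The figures also belong to an adjustment that is unsuitable for the primary analysis.
- **That daily rescreening shows a wide spread in drug start.** Section 4.1 has women "rescreened daily for the development of a new hypertension diagnosis". That governs consent and randomization; drug start follows the pressure criteria.

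**Conclusion.** The point holds as a question of precision. The planned test leaves the stratification factor and a collected pre-drug variable unused. The estimated effect is not distorted and the type I error is not inflated. Under the assumed 24 to 48 h difference by mode of delivery, the normal-theory gain at 66 per arm is about 2 to 7 percentage points at one-sided 0.05 and 3 to 9 at one-sided 0.025. If mode of delivery and the stratum hardly predict stay in this population, the gain is close to nil.

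The gain is most useful if the stated two-tailed 0.05 is taken at its word: unadjusted power at 80 per arm is then 78.5%, and even R² of 0.05 takes it just above 80%. The documents do not support replacing the rank test with a regression on hours for the sake of precision, since stays may be right-skewed and the regression could then have less power.

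**What to change.** Keep delivery to discharge as the endpoint, keep the 24-hour limit and keep the rank-based method. Before any data are reviewed, prespecify the following:

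1. **Primary test.** Subtract 24 h from each stay in the amlodipine arm and apply a rank-sum test stratified by chronic hypertension status and mode of delivery (van Elteren), at a stated one-sided level.
2. **Estimate.** Report the matching stratified Hodges-Lehmann difference, amlodipine minus nifedipine ER, in hours with its confidence interval, and compare the upper limit with 24 h. A plain rank-sum test gives no figure in hours, so this also ties the test to the limit.
3. **Supportive analysis.** Regress hours on arm and the same two factors, with robust or bootstrap standard errors.
4. **Sensitivity analysis only.** Adjust for hours from delivery to the qualifying pressure or first dose, noting that this variable arises after unmasked randomization.

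The cost is a few lines of analysis text, slightly more programming and, for item 4, one timestamp added to the chart abstraction. Some of the four strata may be small, so the plan should say in advance how sparse strata will be merged. Sample size, endpoint and treatment are unaffected.

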2.2 Secondary Objective

Secondary outcomes include the need for additional antihypertensive medications (either increased dose, additional long-acting agents, or additional short-acting agents), patient-

reported side effects, medication discontinuation due to side effects, hospital readmissions, duration of breastfeeding, and breastfeeding continuation and satisfaction.

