PROTOCOL TITLE: Amlodipine versus nifedipine ER for the management of postpartum hypertension: A randomized controlled noninferiority trial

Lead Investigator:

[name]

Prisma Health/University of South Carolina Greenville

Version Date: August 8, 2022

TABLE OF CONTENTS

Table of contents.....	2
Protocol Synopsis.....	3
1 BACKGROUND AND RATIONALE.....	5
2 STUDY OBJECTIVES.....	7
3 INVESTIGATIONAL PLAN.....	8
4 STUDY PROCEDURES.....	9
5 STUDY EVALUATIONS AND MEASUREMENTS.....	12
6 STATISTICAL CONSIDERATIONS.....	13
7 DATA COLLECTION AND MANAGEMENT.....	13
8 REFERENCES.....	13

PROTOCOL SYNOPSIS

Study Title	Amlodipine versus nifedipine ER for the management of postpartum hypertension: A randomized controlled noninferiority trial
Funder	Prisma Health OBGYN Departmental Research Fund
Study Rationale	
-A significant number of pregnancies are complicated by hypertensive disorders (chronic hypertension, gestational hypertension, preeclampsia)-Hypertension is often exacerbated in the postpartum period-Many of these patients require initiation of antihypertensives after delivery-There are a limited number of well-studied treatment options routinely used (labetalol and nifedipine ER)-Prior studies have shown that both labetalol and nifedipine ER are effective-Nifedipine ER has few contraindications, but has significantly more side effects than labetalol-Headache is one of the most commonly reported side effects with nifedipine ER-Headache is also a commonly reported symptom of preeclampsia-Amlodipine is in the same drug class as nifedipine ER, but does not cause headaches-Amlodipine is a first-line antihypertensive in the non-obstetric population-Amlodipine has not been studied in the obstetric population
Study Objectives	
Primary
 
-To evaluate whether amlodipine is noninferior to nifedipine ER in the management of postpartum hypertension 
Secondary
 
-To evaluate whether patients tolerate amlodipine better than nifedipine ER
Study Design	Unmasked, pragmatic randomized controlled trial

Subject Population Inclusion criteria

- English and Spanish-speaking postpartum women with a diagnosis of chronic hypertension, gestational hypertension, or preeclampsia
- Delivery at or beyond 20 weeks' gestation

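### Headache is the most specific reason given to expect better tolerability with amlodipine, yet it is neither a prespecified outcome nor an itemised data field, so a headache comparison would be exploratory and open to uneven ascertainment

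*Combined protocol and SAP*

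**What the plan says.** The synopsis rationale presents headache as a point on which the two drugs differ: "Amlodipine is in the same drug class as nifedipine ER, but does not cause headaches". Section 1 is more cautious, "Headache is not a commonly reported side effect of amlodipine", and gives no amlodipine headache rate. For nifedipine ER it says that "24% of women using nifedipine ER report headache as a side effect". Of headache as a sign of preeclampsia it says that "its presence as a symptom can change patient management", and it adds that drug headache and disease headache are hard to tell apart.

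Section 1 also gives two sets of overall side-effect rates: 48% on nifedipine ER against 20% on labetalol, and 41% on nifedipine ER against 27% on amlodipine.

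The secondary objective in the synopsis is better tolerability, and the hypothesis at the end of section 1 is fewer side effects on amlodipine. Section 2.2 turns this into "reported side effects, medication discontinuation due to side effects", the first of these being reported by the patient. Section 5 has the single line "Side effects reported" in a list introduced as abstracted from the chart, and section 7 says that data are entered from the medical record. Section 3.1 describes the trial as unmasked.

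Headache appears in no objective, outcome, data item or analysis statement. Section 6 gives only the sample size for length of stay, and the synopsis adds only a rank-sum test for noninferiority.

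**The concern.** Two things are at stake.

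**Prespecification.** If headache is later picked out of an open list of side effects, the result is exploratory, even though headache is the effect that the rationale most specifically expects to differ. The broader comparison, any side effect, also counts effects that two drugs of one class may share, and it may well be inconclusive.

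**Ascertainment.** Staff know the assignment, and the protocol tells them that nifedipine ER causes headache and amlodipine does not. The same headache could be charted as a side effect in one arm and as a symptom of preeclampsia in the other, or asked about more often in one arm. Nothing in the plan requires the same question in both arms, and nothing separates a headache present before the first dose from one that starts after it. Uneven charting of this kind could favour amlodipine whatever the drugs do.

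**Working it through.** The plan states no power for side effects or headache, so there is no figure of its own to reproduce. Its 66 per arm (section 6.1) is for length of stay.

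**Inputs from the documents**
- 160 women, 1:1 (sections 3.3 and 3.2), so about 80 per arm, taking the 160 as women who receive study drug.
- 66 per arm (section 6.1) as the lower case.
- Any side effect: 41% versus 27%, and 48% on nifedipine ER (section 1).
- Headache on nifedipine ER: 24% (section 1).

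**Assumptions**
- Two-sided 0.05, as stated for the primary outcome.
- The amlodipine headache rate, which the documents do not give.
- The rate of background disease headache, also not given.

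**Formula.** With d = p1 − p2 and p̄ = (p1 + p2)/2,

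power = Φ{ [d√n − 1.96·√(2p̄(1 − p̄))] / √(p1(1 − p1) + p2(1 − p2)) }

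**Step 1. Any side effect, 41% v 27%, n = 80.** d = 0.14 and p̄ = 0.34. The two square-root terms are 0.670 and 0.663. Then (0.14 × 8.944 − 1.96 × 0.670)/0.663 = −0.09, so power is 46%. About 179 per arm would be needed for 80%.

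**Step 2. Other readings of the protocol's rates**

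| Nifedipine ER v amlodipine | Basis | Power, n = 80 | Power, n = 66 |
|---|---|---|---|
| 41% v 27% | only direct pair | 46% | 40% |
| 48% v 31.6% | 48% × 27/41 | 56% | 49% |
| 48% v 27% | rates from two studies | 79% | 71% |

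**Step 3. Headache attributed to the drug, 24% on nifedipine ER, n = 80**

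| Assumed amlodipine rate | Power |
|---|---|
| 4% | 96% |
| 8% | 79% |
| 10% | 66% |
| 12% | 51% |
| 15.8% (24% × 27/41) | 25% |

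**Step 4. All new or worse headache.** An outcome that does not ask the cause also counts disease headache. If background headache has rate b, independent of drug headache at rate h, the observed rate is 1 − (1 − b)(1 − h). With drug headache 24% v 8% and n = 80:

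| Background b | Observed rates | Power |
|---|---|---|
| 0% | 24.0% v 8.0% | 79% |
| 10% | 31.6% v 17.2% | 56% |
| 20% | 39.2% v 26.4% | 41% |
| 30% | 46.8% v 35.6% | 30% |

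For example, at b = 20%: 1 − 0.80 × 0.76 = 39.2% and 1 − 0.80 × 0.92 = 26.4%.

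**The case against.** The strongest reply is that the listed outcome matches the stated hypothesis. Section 1 predicts fewer side effects, not fewer headaches, and section 2.2 measures side effects. The rationale also gives other reasons for testing amlodipine: few well-studied options, a lower overall side-effect rate and first-line use outside obstetrics. A secondary outcome need not be powered, and the primary conclusion is untouched. All of this stands. It limits the weight of the point but does not supply a named or evenly elicited headache outcome.

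A reader might infer more than the documents support, in four ways:

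- **That headache will not be recorded, or will be merged into one any/none variable.** Sections 2.2 and 5 do not say so. The REDCap form may record side effects by type, and the synopsis has the clinical team assess side effects daily. What is missing is prespecification, a definition and a common way of asking.
- **That the side-effect comparison simply has under 50% power on the protocol's rates.** That is true of the 41% v 27% pair only. Section 1 introduces that evidence as non-obstetric, whereas the 48% comes from the study of labetalol and nifedipine in postpartum hypertension and gives 56% to 79%.
- **That naming headache secures 79% to 96% power.** Those figures are for drug-attributed headache at assumed amlodipine rates of 8% down to 4%. Counting every new or worse headache brings in disease headache, and with 20% background the 79% falls to 41%. The 24% may itself already contain some disease headache, so step 4 is an illustration rather than a forecast.
- **That magnesium use should become a secondary outcome because the rationale implies it would change.** The rationale never mentions magnesium. It says only that headache can alter management, and section 5 already collects magnesium use.

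**Conclusion.** The point holds as a gap in prespecification and ascertainment. Headache is the most specific effect on which the drugs are expected to differ, and the plan neither names it nor requires that it be asked about in the same way in both arms. In an unmasked trial with chart-abstracted side effects, a later headache result would be exploratory and could reflect uneven charting. This does not depend on any power figure.

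Low power for any side effect is supporting evidence only: 46% at 80 per arm on the direct pair, and 56% to 79% with the 48% rate. These figures assume two-sided 0.05 and 80 treated women per arm. The tolerability objective is affected; the length-of-stay analysis is not.

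**What to change.** In section 2.2, add headache that is new or worse after the first study-drug dose (yes/no) as a prespecified secondary tolerability outcome, alongside any side effect, and state the period it covers. In section 5, add one field for headache before the first dose and one for headache after it, filled from a standard question put in the same words in both arms. The outcome should not depend on anyone's view of the cause, since attribution is where knowledge of the assignment could enter most easily.

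The cost is protocol wording, a short question for staff to ask, and one or two REDCap fields, with no more women. There are two limits. Avoiding attribution lets disease headache dilute the contrast, so power may be no better than for any side effect. A common question also does not remove the influence of the woman knowing her own drug.
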